## 13.3.1. Efficacy analysis

The primary efficacy parameter is Change from baseline in weekly frequency of Spontaneous Bowel Movement (SBMs).

The primary efficacy analysis the proportion of 2-week SBM Overall Responders will be compared to the proportion in the placebo group using the CMH test.

The secondary efficacy parameters are:

- 1. Proportion of patients with complete spontaneous bowel movement (CSBM)
- 2. Proportion of patients with a SBM within 24 h after the first dose of study drug
- 3. Median time to first SBM
- 4. Change from baseline in Stool consistency using Bristol Stool Form Scale (BSFS)
- 5. Change from Baseline in Weekly Degree of Straining of SBMs
- 6. Change from Baseline in Weekly Abdominal Bloating Score
- 7. Change from Baseline in Weekly Abdominal Discomfort Score

For each of the above secondary efficacy parameters, Elobixibat dose group will be compared to the placebo group using an analysis of covariance (ANCOVA) model with fixed effect terms for treatment group and the patient's corresponding baseline value of the parameter as a covariate. The overall type I family-wise error rate for testing the primary and secondary efficacy parameters will be controlled at the 0.05 significance level using the following five-step serial gatekeeping multiple comparisons procedure (MCP).

All hypothesis tests will be two-sided.

The first step will test the primary efficacy parameter for the Elobixibat 5mg dose group at the 0.05 significance level

The second step will test the primary efficacy parameter for the 5mg Elobixibat dose group and the first five secondary parameters (i.e., SBM, CSBM, stool consistency, severity of straining, and constipation severity).

The third step will test the last two secondary parameters (i.e., bloating, abdominal discomfort) for the Elobixibat 5mg dose group. The two individual hypotheses within this step will be tested using an overall type I error rate of 0.05 by means of a Hochberg procedure to control for multiple parameters.

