#### Criteria for Evaluation: Efficacy

# **Primary Endpoint:**

- 1. Change from baseline in weekly frequency of Spontaneous Bowel Movement (SBMs), Time Frame: From Baseline to 2 weeks.
- SBM is defined as the bowel movement occurring in the absence of laxative use or manual disimpaction in last 24 hours

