## **6.3. Efficacy Variables**

#### **6.3.1.** Primary efficacy variables

- Change from baseline in weekly frequency of Spontaneous Bowel Movement (SBMs)
  - SBM is defined as bowel movement occurring in the absence of laxative use or manual disimpaction in last 24 hours
  - Change from baseline in the frequency of SBM per week.

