#### **6.3.2.** Secondary Efficacy variables

- 1. Proportion of patients with complete spontaneous bowel movement (CSBM)
  - CSBM is defined as SBM that is associated with a sense of complete evacuation.
  - A CSBM responder is defined as a patient with ≥3 CSBMs per week and an increase of ≥1 CSBM per week from Baseline.

- 2. Proportion of patients with a SBM within 24 h after the first dose of study drug
- 3. Median time to first SBM
  - SBM is defined as a bowel movement that occurred in the absence of a laxative use or manual disimpaction.
  - Baseline value for the number of SBM is defined as the average of the numbers of SBM per week for over the 2-week pretreatment Period.
- 4. Change from baseline in Stool consistency using Bristol Stool Form Scale (BSFS)
- Change from baseline in weekly Stool Consistency using BSFS score, Time
   Frame: From baseline to 2 weeks
- The stool consistency is measured using the seven-point ordinal BSFS score.
- The BSFS classifies human stool into seven types and points them accordingly:
  - o Type 1: Separate hard lumps, like nuts (hard to pass)
  - o Type 2: Sausage-shaped, but lumpy
  - o Type 3: Like a sausage but with cracks on its surface
  - o Type 4: Like a sausage or snake, smooth and soft
  - o Type 5: Soft blobs with clear cut edges (passed easily)
  - o Type 6: Fluffy pieces with ragged edges, a mushy stool
  - Type 7: Watery, no solid pieces, entirely liquid
- Types 1 and 2 indicate constipation, with 3 and 4 represents the ideal stool form (especially the latter), and 5, 6 and 7 tends towards diarrhoea.
- For a given assessment week, the weekly stool consistency is defined as the sum of non-missing stool consistency score for SBMs during that week divided by the number of non-missing stool consistency score for SBMs during that week.
- 5. Change from Baseline in Weekly Degree of Straining of SBMs
- The degree of straining is measured using the five-point ordinal scale (1=Not at all, 2=A little bit, 3=A moderate amount, 4=A great deal, and 5=An extreme amount).
- For a given assessment week, the weekly degree of straining is defined as the sum of non-missing straining score for SBMs during that week divided by the number of non-missing straining score for SBMs during that week.

- 6. Change from Baseline in Weekly Abdominal Bloating Score
- The abdominal pain score is measured using the five-point ordinal scale (1=None, 2=Mild, 3=Moderate, 4=Severe, and 5=Very severe).

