## 13.2. Sample Size Estimation

A total of 150 patients with chronic constipation will be enrolled in the study.

Assuming a significance level of 2.5% and a power of 95%, we require 60 completed subjects per treatment group (a total of 120 subjects in study) to prove superiority of Elobixibat.

Assuming ~20% drop-out rates, 150 subjects will be randomized in this study with 1:1 ratio (75 subjects per each arm) to Elobixibat 5mg vs Placebo.

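### Section 13.3.1 defines a continuous primary endpoint but names a CMH test of an undefined SBM responder as its primary analysis

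*Protocol*

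**What the plan says.** - **Endpoint.** The synopsis gives the primary endpoint as "Change from baseline in weekly frequency of Spontaneous Bowel Movement (SBMs), Time Frame: From Baseline to 2 weeks". Section 4.3.1 repeats it, section 6.1 lists it first, and section 6.3.1 describes it as "Change from baseline in the frequency of SBM per week". Section 13.3.1 opens in the same way.
- **Primary analysis.** The next sentence of section 13.3.1 sets out how the primary comparison is made: "the proportion of 2-week SBM Overall Responders will be compared to the proportion in the placebo group using the CMH test".
- **Responder definition.** The only one in the protocol (synopsis and section 6.3.2) belongs to a secondary endpoint: "A CSBM responder is defined as a patient with ≥3 CSBMs per week and an increase of ≥1 CSBM per week from Baseline".
- **ANCOVA.** It is reserved for the secondaries: "For each of the above secondary efficacy parameters, Elobixibat dose group will be compared to the placebo group using an analysis of covariance (ANCOVA) model". Baseline enters as a covariate.
- **Gatekeeping.** "The first step will test the primary efficacy parameter for the Elobixibat 5mg dose group at the 0.05 significance level". No method is named. Step 2 tests the primary parameter a second time, together with five parameters it calls secondary, and SBM is the first of them.
- **Sample size.** Section 13.2 says: "Assuming a significance level of 2.5% and a power of 95%, we require 60 completed subjects per treatment group". It gives no endpoint, difference, SD or responder rates, and does not say whether the 2.5% is one-sided or two-sided.

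**The concern.** A proportion of responders is a different quantity from a mean change in weekly frequency. It answers a different question and can give a different result on the same diaries. If section 13.3.1 is followed literally, the confirmatory test does not estimate the endpoint defined in the synopsis and sections 4.3.1 and 6.3.1. It also cannot be run from the protocol alone, because the rule that makes a patient an SBM responder is missing. That rule would first be fixed in an SAP that section 13.3 allows to be finalised at any time before database lock.

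The single superiority claim depends on this test. An SAP that follows the CMH sentence departs from the endpoint, and one that follows the endpoint departs from the named primary analysis. Either choice is open to challenge when the result is read.

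**Working it through.** **Step 1. Is a single decision test identifiable?** Putting the statements side by side:

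- Endpoint, in the synopsis, 4.3.1, 6.1, 6.3.1 and the first sentence of 13.3.1: continuous change in weekly SBM frequency.
- Named primary analysis, second sentence of 13.3.1: CMH on a binary SBM responder, undefined.
- ANCOVA, 13.3.1: secondaries only, so no method is expressly attached to the SBM change as primary.
- Gatekeeping step 1: the primary parameter, method not named.
- Gatekeeping step 2: the primary parameter again, plus SBM as a secondary.

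No statement overrides the others, so the conflict stands without any arithmetic.

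**Step 2. Does the sample size settle it?** The dropout step reproduces: 60/(1 − 0.20) = 75 per arm and 120/(1 − 0.20) = 150, as stated. The 60 per arm cannot be reproduced, because no effect, SD or rates are given. It can only be solved backwards:

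- Normal approximation, two-sided 5% (the same as one-sided 2.5%), 95% power: d = (1.960 + 1.645) × √(2/60) = 0.658 SD.
- With the t distribution on 118 degrees of freedom: d = 0.664 SD.

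This is what 60 per arm can detect in an unadjusted t-test. It does not show which test the sponsor had in mind.

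**Step 3. How different are the two tests? (Illustration; normal model assumed.)** Take d = 0.664 and call a patient a responder above a cut that gives placebo rate p0. Then p1 = Φ(Φ⁻¹(p0) + d). With a single stratum, CMH behaves like the chi-square test, so with p̄ = (p0 + p1)/2:

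power = Φ{[(p1 − p0) − 1.96 × √(2p̄(1 − p̄)/60)] / √([p0(1 − p0) + p1(1 − p1)]/60)}

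Example, p0 = 0.30: p1 = Φ(−0.524 + 0.664) = 0.555 and the difference is 0.255. The null SE is 0.0903 and the alternative SE is 0.0873. Power = Φ[(0.2553 − 0.1770)/0.0873] = Φ(0.897) = 0.82.

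| Placebo rate | 20% | 30% | 40% | 50% | 60% | 70% |
|---|---|---|---|---|---|---|
| Power, 60 per arm | 78% | 82% | 82% | 80% | 77% | 70% |

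For 95% power the responder test would need about 20% vs 51%, 30% vs 62%, 40% vs 72% or 50% vs 81%.

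**Step 4. Does the loss depend on the model?** Yes. Simulation with 60 per arm, two-sided 5%, 20,000 replicates and assumed distributions:

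- Lognormal, log-SD 1.0, log-shift 0.9: t-test 96%; responder cuts at placebo rates 25–50%, 96–97%.
- Lognormal, log-SD 0.8, log-shift 0.64: t-test 96%; responder cuts at placebo rates 19–50%, 91–94%.
- Laplace, shift 0.66 SD: t-test 95%; responder cuts at placebo rates 31–50%, 95–99%.

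**The case against.** The best defence is that gatekeeping step 1 tests the primary efficacy parameter, which section 13.3.1 has just defined as the SBM change, and that SBM in step 2 sits among parameters given ANCOVA. On that reading the CMH sentence is a stray and the SAP would tidy it up. This has some force: the decision test is contradictory, not settled as CMH. It does not remove the problem. Step 1 names no method, the only sentence that names the primary analysis says CMH, and a later SAP does not change what the protocol states.

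Four stronger readings are tempting, and the documents do not support them:

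- **That the stated 95% power cannot hold for both tests.** This is true only under an assumed distribution. Weekly SBM frequency is a count with baseline restricted to below 3 per week (section 5.1), so skew is plausible, and step 4 of the working shows the loss can vanish.
- **That the cut-off could be chosen after treatment results are seen.** Section 13.3 has the SAP final before database lock. Section 12.4.2.2 breaks the overall code only after data entry, query resolution and assignment to analysis sets. The residual risk is a choice made on blinded data.
- **That 2.5% in section 13.2 conflicts with two-sided 0.05 in section 13.3.1.** They agree if 2.5% is one-sided, a natural reading for a superiority trial. It only needs to be said.
- **That CMH necessarily drops baseline adjustment.** The strata are not stated, so this cannot be concluded.

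**Conclusion.** The contradiction is real and should be corrected before unblinding. The protocol defines one primary endpoint and names a primary analysis of a different, undefined one, and nothing else in the document resolves which decides the trial. This conclusion rests on the text alone.

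The size of the consequence cannot be fixed from the document. The 70–82% against 95% comparison assumes a normal shift of 0.66 SD, a single stratum, 60 completers per arm and placebo responder rates of 20–70%. It shows that the choice of test can matter, not that this trial is underpowered. The missing planning assumptions and the unstated sidedness in section 13.2 are secondary. They matter here only because they leave the sample size unable to show which test was meant.

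**What to change.** 1. **Section 13.3.1, primary analysis.** Replace the CMH sentence. Compare the change from the 2-week pretreatment average to weekly SBM frequency over one fixed treatment window, by ANCOVA with treatment and baseline SBM frequency, two-sided 5%. The 2-week treatment average is one suitable window, since it mirrors the baseline definition in the synopsis and section 6.3.2.
2. **SBM responder.** Delete the test, or define the rule in full and label it supportive. Making a defined SBM responder the primary endpoint would also be coherent, but it would mean rewriting the endpoint in every section that now states the change.
3. **Gatekeeping.** Name the ANCOVA in step 1. Remove the primary parameter and SBM from step 2, and correct its count of five secondaries.
4. **Section 13.2.** State that 2.5% is one-sided, equal to two-sided 5%. Tie the 60 per arm to this test with the difference and SD the sponsor actually assumed. The 0.66 SD above is back-solved from the sample size and must not be entered as the justification.

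Cost: a protocol amendment, which under section 7.4 needs sponsor agreement and documented ethics committee approval, completed before unblinding. No extra patients, visits or data are needed.

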# **Secondary Efficacy Endpoints:**

- 1. Proportion of patients with complete spontaneous bowel movement (CSBM)
- 2. Proportion of patients with a SBM within 24 h after the first dose of study drug
- 3. Median time to first SBM
- 4. Change from baseline in Stool consistency using Bristol Stool Form Scale (BSFS)
- 5. Change from Baseline in Weekly Degree of Straining of SBMs
- 6. Change from Baseline in Weekly Abdominal Bloating Score
- 7. Change from Baseline in Weekly Abdominal Discomfort Score

#An SBM is a BM that occurs in the absence of laxative, suppository, or enema use 24 hour of the BM or the calendar day before the BM

#A CSBM is an SBM that is associated with a sense of complete evacuation.

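### The multiplicity procedure in Section 13.3.1 claims family-wise error of 0.05, but as written it does not secure this for the secondary endpoints

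*Protocol*

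**What the plan says.** Protocol Section 13.3.1 (Efficacy analysis) makes an explicit claim: "The overall type I family-wise error rate for testing the primary and secondary efficacy parameters will be controlled at the 0.05 significance level". It then sets out the means of delivering it, which it describes as a "five-step serial gatekeeping multiple comparisons procedure (MCP"). It adds: "All hypothesis tests will be two-sided".

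Three steps follow.

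- **Step 1:** "The first step will test the primary efficacy parameter for the Elobixibat 5mg dose group at the 0.05 significance level".
- **Step 2:** the primary parameter again, together with "the first five secondary parameters (i.e., SBM, CSBM, stool consistency, severity of straining, and constipation severity"). No significance level, testing order or adjustment is given.
- **Step 3:** "The third step will test the last two secondary parameters (i.e., bloating, abdominal discomfort) for the Elobixibat 5mg dose group". These two hypotheses share an overall 0.05 by Hochberg.

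The same section numbers seven secondary parameters, matching Section 4.3.1. The second is "Proportion of patients with a SBM within 24 h after the first dose of study drug". The others are CSBM (first), time to first SBM as a median (third), stool consistency (fourth), straining (fifth), bloating (sixth) and abdominal discomfort (seventh).

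**The concern.** Gatekeeping controls family-wise error only if three things are fixed in advance: which hypotheses sit in each step, how error is shared within a step, and what must be significant before the next step opens. For step 2 the protocol leaves the second unstated and contradicts itself on the first. For step 3 it does not write down the third.

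Two analysts could follow Section 13.3.1 faithfully and test different families at different levels. Choosing between readings after unblinding would defeat the purpose of pre-specification, and any secondary claim would then rest on an error rate that the text does not establish. Two listed secondaries, SBM within 24 hours and time to first SBM, are named in no step, so it is unclear whether a claim on them is covered at all.

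**Working it through.** **1. Step 2 set against the numbered list in the same section**

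| Listed secondary | Named in step 2? |
|---|---|
| 1. CSBM | yes |
| 2. SBM within 24 h | no |
| 3. Median time to first SBM | no |
| 4. Stool consistency | yes |
| 5. Straining | yes |
| (primary) weekly SBM frequency | yes, as SBM, besides the explicit repeat of the primary |
| (not an endpoint) constipation severity | yes |

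Constipation severity is absent from the endpoint lists (Synopsis, Sections 4.3.1, 6.1 and 6.3), the diary items reviewed at Visits 2 to 4 (Sections 7.1.2 to 7.1.4) and the Schedule of Events (Table 1). It would yield no p-value. The bracketed list therefore contains three testable secondaries (CSBM, stool consistency, straining), while the words before it point to five.

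**2. Where the stated 0.05 is reproduced**

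Suppose every null is true and step 2 opens only after step 1 succeeds, as serial gatekeeping implies. Any false claim then requires a false positive on the single step 1 test, so family-wise error is 0.05. Simulation with 400,000 draws agrees (0.049 to 0.051).

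**3. Where it is not secured**

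Assumptions, none stated in the protocol: the primary effect is real and step 1 succeeds; all step 2 secondaries are null; each is tested at two-sided 0.05.

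For k independent tests, P(at least one false claim) = 1 − 0.95^k:

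- k = 3: 1 − 0.8574 = 0.143
- k = 5: 1 − 0.7738 = 0.226

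For z statistics with common correlation ρ and c = 1.96, the probability is 1 − ∫ φ(t) [Φ((c − √ρ·t)/√(1−ρ)) − Φ((−c − √ρ·t)/√(1−ρ))]^k dt, evaluated numerically:

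| Step 2 family | independent | ρ = 0.5 | ρ = 0.7 |
|---|---|---|---|
| three named testable secondaries | 14.3% | 12.5% | 10.9% |
| listed secondaries 1 to 5 | 22.6% | 18.3% | 14.8% |

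Two variations:

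- If step 1 succeeds with 95% probability, the independent figures become 0.143 × 0.95 = 13.5% and 0.226 × 0.95 = 21.5%.
- If step 3 opened whatever happened in step 2, its Hochberg pair adds a further 0.05 under independence: 1 − 0.95^4 = 18.5% and 1 − 0.95^6 = 26.5%.

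**4. With the rule of step 3 applied to step 2**

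Hochberg at an overall 0.05 over five null secondaries gives a simulated error of 4.9% (independent), 4.3% (ρ = 0.5) and 3.1% (ρ = 0.8). The claimed level is attainable with a rule that the text does not contain.

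**The case against.** The best defence has three parts. The section is silent on a step 2 adjustment rather than excluding one; its opening sentence claims overall control; and a separate SAP, not shown here, may supply the rule. The first two are right as far as they go. The text does not say that each step 2 test is run at 0.05, and it cannot be said that the error rate will in fact be uncontrolled. But the protocol sets out the procedure itself, gives step 3 its own within-step rule, and in Section 13.3 defers specifically only the handling of missing, unused and spurious data. An SAP could repair the gap, but it would also have to correct the step count and the endpoint list that the protocol states.

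Several stronger readings are tempting and are not supported:

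- **That 22.6% is the error rate of the plan.** It requires ignoring the bracketed list and assuming 0.05 per test. On the bracketed list, SBM is the primary and constipation severity cannot be tested, which leaves three tests and 14.3%.
- **That the trial's primary conclusion is at risk from this fault.** Step 1 protects the primary test and the global null.
- **That several named endpoints do not exist.** Only constipation severity is absent.
- **That the wrong names inflate the error.** They leave the family undefined; inflation would come from testing within step 2 without adjustment.
- **That the gate to step 3 cannot be passed.** No opening condition is written, so none can be said to fail. The fault is that it is missing.

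**Conclusion.** The point holds in a limited form. The procedure in Section 13.3.1 does not secure the family-wise error of 0.05 that it claims for secondary endpoints. Five steps are announced and three given; step 2 repeats the primary and has no rule for sharing error; its named contents contradict its own description; and the condition for reaching step 3 is unwritten.

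On the assumptions shown, the chance of at least one false secondary claim is about 11% to 14% for the three named testable secondaries, or about 15% to 23% if listed secondaries 1 to 5 are meant, over correlations from 0.7 down to independence. These figures show what the text permits; they do not predict what will be done. Inference on the primary endpoint is not affected by this fault, although step 1 itself needs one clarification, given under the fix.

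**What to change.** Amend Section 13.3.1 before unblinding so that it reads as three steps:

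1. Test the primary at two-sided 0.05. First reconcile what the primary is: the section names change in weekly SBM frequency as the primary parameter, then describes the primary analysis as a CMH comparison of SBM responders. Until one is chosen, the first gate is ambiguous.
2. If step 1 is significant, test listed secondaries 1 to 5 (CSBM response, SBM within 24 hours, time to first SBM, stool consistency, straining) by Hochberg at an overall 0.05, the method step 3 already uses.
3. Only if all five are significant, test bloating and abdominal discomfort by Hochberg at an overall 0.05. This opening condition is a choice to be written in; the present text does not fix one.

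Delete the five-step label, the repeated primary test, SBM as a secondary, and constipation severity.

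The change is wording only and needs no new data. The price is some power for individual secondaries: a step 2 endpoint that succeeds alone must reach 0.05/5 = 0.01, and one failure in step 2 closes step 3.

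Separately, the 5 mg dose-group label in this section and the dosing descriptions elsewhere in the protocol must be reconciled. That does not bear on error control.

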## 13.3.2. Safety Analysis

The safety analysis will be performed using the Safety Population. The safety parameters include AEs, clinical laboratory parameters, vital signs, and ECG parameters. For each safety parameter, the last assessment made before randomization will be used as the baseline for all analyses of that safety parameter.

# 13.4. Data handling

All clinical data generated during the conduct of the study will be entered in the source notes and will be transcribed in the respective case record form (CRF). The computer-

generated randomization schedule will also be treated as raw data. All raw data and transcribed data forms compiled by the study personnel assisting in the study will be checked for completeness. All data related to the project will be in the custody of the Principal Investigator or Project Manager until transferred to archives.

The detail regarding CRF completion requirements, correction requirements, including who is authorized to make corrections on the CRF and how queries about study data are handled will be available in data management plan. All raw data generated during the conduct of the project compiled by the study personnel assisting in the study will be checked for completeness. Biostatistics department after receipt of the raw data will perform a statistical analysis and statistical data will be generated which will be further sent for compilation of the final clinical study report of the study.

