#### 4. STUDY DESIGN & PLAN OF STUDY

## 4.1. Overview of the Study design

Study Type: Interventional

Study Design: Prospective, multicenter, randomized, double blind, parallel group, placebo controlled, phase III superiority study

Randomization: Subjects meeting the inclusion criteria and none of the exclusion criteria will be randomized to either of the 2 arms i.e. test arm or placebo arm.

The packaging of the test and placebo products will be similar in appearance to make differences in treatment less obvious to the subjects and to maintain adequate blinding of evaluators. Neither the subject nor the investigator will be able to identify the treatment. The containers will not be opened by the subject at the study center.

Method of Generating Random Sequence: Computer generated randomization.

Method of Concealment: Sequentially numbered, sealed, opaque envelopes.

Blinding/Masking: Double Blind

Dosing Schedule:

• Test Arm: Elobixibat tablet

The usual adult dosage is 10 mg of Elobixibat self-administered orally once daily before breakfast. The dose may be adjusted according to the patient's response, but the maximum daily dose is 15 mg. Therefore, Elobixibat tablet (10 mg oral once daily self-administered as two tablets of 5 mg) in patients with chronic constipation once daily for one week and then dose titration (up or down) will be done according to the patient's response.

• Comparator Arm: Placebo matching test product

Placebo tablet matching test product (10 mg oral once daily self-administered as two tablets of 5 mg) in patients with chronic constipation once daily for one week and then dose titration of placebo (up or down) will be done according to the patient's response.

Trial visits:

Visit 1# (Screening visit Day -28 to Day -15)

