#### 12.4.1. Randomization

The randomization codes will be generated by the Randomization Code Administrator, an individual within Statistical Programming who will generate the randomization codes and will not be assigned the role of Statistical Programmer for this study. The randomization codes will be provided in a secure manner.

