## 12.4.2.2. Unblinding for Regulatory and Analysis requirement at the end of study

For regulatory requirement, reporting of SAEs not previously unblinded at the site level, the blind will be broken for SAEs, in case of requirement.

The overall randomization code will be broken only when all final clinical data have been entered onto the database and all data queries have been resolved, and the assignment of subjects to the analysis sets has been completed.

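### Section 13.4 puts the randomisation schedule in the custody of the Principal Investigator or Project Manager, which contradicts the blinding rules in 4.1, 12.4.1 and 12.4.2.2

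*Protocol*

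**What the plan says.** Section 13.4 of the protocol (Data handling) deals with source notes, case record forms and custody. On the computer-made allocation list it states: "generated randomization schedule will also be treated as raw data". The next sentence is: "All raw data and transcribed data forms compiled by the study personnel assisting in the study will be checked for completeness". The one after that is: "All data related to the project will be in the custody of the Principal Investigator or Project Manager until transferred to archives". No clause treats the schedule differently from other data. What 13.4 passes to the data management plan is case record form completion, corrections and queries. Custody is not passed on; it is settled here.

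Three other sections describe a blinded trial:

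- Section 4.1 gives "Method of Generating Random Sequence: Computer generated randomization" and "Method of Concealment: Sequentially numbered, sealed, opaque envelopes", and states: "Neither the subject nor the investigator will be able to identify the treatment".
- Section 12.4.1 assigns generation of the codes to a Randomization Code Administrator, who "will not be assigned the role of Statistical Programmer for this study". The codes are then to be passed on securely; the recipient is not named.
- Section 12.4.2.2 states: "The overall randomization code will be broken only when all final clinical data have been entered onto the database". It adds two further conditions: all queries resolved, and subjects assigned to their analysis sets.

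**The concern.** A schedule held during the trial by someone who should be blinded undoes two separate safeguards. Sight of future allocations removes concealment and can influence who is enrolled and when. Sight of current allocations removes the blind.

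Both matter here because much of the outcome depends on judgement. The primary endpoint is a count of spontaneous bowel movements taken from patient diaries, which site staff collect and review at each visit (sections 7.1.2 to 7.1.4). Dose is adjusted after one week according to response (section 4.1). Rescue medicine may be used when symptoms become intolerable, and bowel movements within 24 hours after rescue are not counted for efficacy (section 5.4). Each of these steps could be influenced by knowledge of the arm.

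**Working it through.** No figure is at issue, so the check sets the clauses side by side.

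1. **Does the custody clause reach the schedule?** Yes, by two routes. Section 13.4 names the schedule as raw data. Even without that sentence, the schedule is data related to the project, and the custody clause covers all such data.

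2. **Who may hold it?** The Principal Investigator or the Project Manager. The first is an investigator, so section 4.1 applies directly: a person holding the list can identify every treatment. The protocol gives the Project Manager no enrolling, dosing or assessing role and does not say whether that person is blinded. Section 12.4.2.2, however, restricts the overall code by time and not by role, so early possession by the Project Manager also fits badly with it.

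3. **When?** The clause gives an end point (transfer to archives) but no starting point. The surrounding text concerns data generated during study conduct, and nothing delays custody of the schedule until after unblinding. Section 12.4.2.2 permits release only once its three conditions are met. On the literal reading, the two periods conflict.

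4. **Does another section settle custody?** Section 12.4.1 says who generates the codes and that they are passed on securely, but not who keeps the list. Section 13.4 is the only place that assigns custody of the schedule.

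5. **Do the other safeguards cure it?** They do not.
   - The locked storage in section 15 keeps out unauthorised people, whereas 13.4 makes the Principal Investigator an authorised holder.
   - Similar packaging (4.1) does not blind a person who has the list.
   - The records required in 12.4.2 and 12.4.2.1 cover opened envelopes and accidental unblinding, not routine possession of the whole schedule.

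6. **Reach.** Section 13.2 randomises 150 patients, 75 + 75 = 150. A holder of the complete schedule would know all 150 allocations, past and future. The protocol offers no basis for turning this into a bias in the treatment effect, and none is claimed.

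**The case against.** The strongest reply is that 13.4 is a general archiving clause and the specific clauses should govern. Codes come from a separate administrator, are passed on securely and are released only at the end, so a sensible team would never hand the list to an investigator. The clause also says Principal Investigator **or** Project Manager, and the latter has no stated role in enrolment or assessment. This limits what may be concluded: the text permits the breach but does not require it. It does not remove the contradiction, because no rule of precedence is given and 13.4 names the schedule expressly.

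Three stronger readings are tempting, and the protocol does not support them.

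- *Site staff check the list.* A reader might infer this from the completeness sentence. That sentence says study personnel compile the raw data. It names no checker, and the schedule is produced by the Randomization Code Administrator.
- *Allocation runs on envelopes opened at site, so concealment is weak.* Section 4.1 gives no location, holder or contents for the envelopes, and section 7.1.2 lists treatment allocation at Visit 2 without mentioning them. The only envelopes expressly sent to sites are the code-break envelopes of 12.4.2, which already carry controls: date, time and reason are recorded, accidental unblinding is a major deviation, and monitors check. Sequentially numbered, sealed, opaque envelopes are a recognised method of concealment. Replacing them with coded kits would be a preference, and the unstated logistics are missing detail, not an error.
- *Neither concealment nor the blind is protected.* Matching placebo, similar packaging, a separate code administrator, code-break controls and delayed release of the code are all written into the protocol.

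**Conclusion.** The point holds as an internal contradiction. Section 13.4, as worded, allows the full randomisation schedule to be held during the trial by a Principal Investigator whom section 4.1 blinds, and by either named holder before section 12.4.2.2 allows the overall code to be opened. If acted on, it exposes the allocations of all 150 patients; the effect on the results cannot be quantified.

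The conclusion assumes that the custody clause means what it says and applies from the time the schedule exists. If the sponsor intended custody to begin only after unblinding, the conflict disappears, but the text does not say so. Nothing in the protocol shows that an investigator has held or will hold the list, and the finding does not put the double-blind design as a whole in doubt. It should nevertheless be corrected, because the clause is wrong as written and bears directly on the blind.

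**What to change.** Amend section 13.4 to state that the randomisation schedule is excluded from the custody of the Principal Investigator and the Project Manager. State that it stays solely with the Randomization Code Administrator named in 12.4.1, or with another custodian independent of trial conduct, until the conditions in 12.4.2.2 are met. From then on it can be treated and archived as raw data with the rest. The individual code-breaks in 12.4.2 and the provision for serious adverse events in 12.4.2.2 can stand unchanged.

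The cost is one sentence of protocol wording, with the sponsor agreement and ethics committee review that section 7.4 requires for a protocol change. It needs no added patients, visits, assessments or changes to supplies.
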